7.0 TRIAL PROCEDURES

7.1 Trial Procedures

The Trial Flow Chart - Section 6.0 summarizes the trial procedures to be performed at each visit. Individual trial procedures are described in detail below. It may be necessary to perform these procedures at unscheduled time points if deemed clinically necessary by the investigator.

7.1.1 Administrative Procedures

7.1.1.1 Informed Consent

The Investigator or qualified designee must obtain documented consent from each potential participant prior to participating in a clinical trial.

Consent must be documented by the participant's dated signature or by the participant's legally acceptable representative's dated signature on a consent form along with the dated signature of the person conducting the consent discussion.

A copy of the signed and dated consent form should be given to the participant before participation in the trial.

The initial informed consent form, any subsequent revised written informed consent form and any written information provided to the participant must receive the IRB/ approval/. The participant or his/her legally acceptable representative should be informed in a timely manner if new information becomes available that may be relevant to the participant's willingness to continue participation in the trial. The communication of this information will be provided and documented via a revised consent form or addendum to the original consent form that captures the participant's dated signature or by the participant's legally acceptable representative's dated signature.

Specifics about a trial and the trial population will be added to the consent form template by the Project Manager/sponsor team.

The informed consent will adhere to IRB/ requirements, applicable laws and regulations and Sponsor requirements.

7.1.1.2 Inclusion/Exclusion Criteria

All inclusion and exclusion criteria will be reviewed by the investigator or qualified designee to ensure that the participant qualifies for the trial.

7.1.1.3 Medical History

A medical history will be obtained by the investigator or qualified designee. Medical history will include all active conditions, and any condition diagnosed within the prior 10 years that are considered to be clinically significant by the Investigator. Details regarding the disease for which

the participant has enrolled in this study will be recorded separately and not listed as medical history.

7.1.1.4 Prior and Concomitant Medications Review

7.1.1.4.1 Prior Medications

The investigator or qualified designee will review prior medication use, including any protocol-specified washout requirement, and record prior medication taken by the participant within 28 days before starting the trial. Treatment for the disease for which the participant has enrolled in this study will be recorded separately and not listed as a prior medication.

7.1.1.4.2 Concomitant Medications

The investigator or qualified designee will record medication, if any, taken by the participant during the trial. All medications related to reportable SAEs and events of clinical interests should be recorded as defined in Section 7.2.

7.1.1.5 Disease Details and Treatments

7.1.1.5.1 Disease Details

The investigator or qualified designee will obtain prior and current details regarding disease status.

7.1.1.5.2 Prior Treatment Details

The investigator or qualified designee will review all prior cancer treatments including systemic treatments, radiation and surgeries

7.1.1.5.3 Subsequent Anti-Cancer Therapy Status

The investigator or qualified designee will review all new anti-neoplastic therapy initiated after the last dose of trial treatment. If a participant initiates a new anti-cancer therapy within 30 days after the last dose of trial treatment, the 30-day Safety Follow-up visit must occur before the first dose of the new therapy. Once new anti-cancer therapy has been initiated the participant will move into survival follow-up.

7.1.1.6 Assignment of Study ID

All consented participants will be given a unique study ID that will be used to identify the participant for all procedures that occur. Each participant will be assigned only 1 study ID. Screening numbers must not be re-used for different participants.

7.1.1.7 Assignment of Allocation Number

The study ID as described above will be used throughout the length of participation.

7.1.1.8 Trial Compliance (Medication/Diet/Activity/Other)

Lenvatinib: Lenvatinib 20 mg (two 10-mg capsules) once daily will be taken orally with water (with or without food) at approximately the same time each day in 21-day cycles. If a lenvatinib dose is missed and cannot be taken within 12 hours, then that dose should be skipped and the next dose should be taken at the usual time of administration.

Lenvatinib compliance will be calculated by the Sponsor based on the drug accountability documented by the site staff and monitored by the Sponsor/designee. The objective is 100% compliance and investigators and their staff should evaluate compliance at each visit and take appropriate steps to optimize compliance.

Pembrolizumab: Pembrolizumab will be administered as a 30-minute IV infusion on Day 1 of each 21-day cycle. Sites should make every effort to target infusion timing to be as close to 30 minutes as possible. However, given the variability of infusion pumps from site to site, a window of –5 minutes and +10 minutes is permitted (ie, infusion time is 30 minutes [–5 min/+10 min]).

After Cycle 1 Day 1, pembrolizumab may be administered up to 3 days before or after the scheduled Day 1 of each subsequent cycle due to administrative reasons.

Administration of pembrolizumab will be witnessed by the investigator and/or qualified designee. The total volume of study intervention infused will be compared with the total volume prepared to determine compliance with each dose administered.

7.1.2 Clinical Procedures/Assessments

7.1.2.1 Adverse Event (AE) Monitoring

The investigator or qualified designee will assess each participant to evaluate for potential new or worsening AEs as specified in the Trial Flow Chart and more frequently if clinically indicated. Adverse experiences will be graded and recorded throughout the study and during the follow-up period according to NCI CTCAE Version 5.0 (see Appendix 2). Toxicities will be characterized in terms regarding seriousness, causality, toxicity grading, and action taken with regard to trial treatment.

Please refer to section 7.2 for detailed information regarding the assessment and recording of AEs.

7.1.2.2 Full Physical Exam

The investigator or qualified designee will perform a complete physical exam during the screening period. Clinically significant abnormal findings should be recorded as medical history. A full physical exam should be performed during screening,

7.1.2.3 Directed Physical Exam

For cycles that do not require a full physical exam per the Trial Flow Chart, the investigator or qualified designee will perform a directed physical exam as clinically indicated prior to trial treatment administration.

7.1.2.4 Vital Signs

The investigator or qualified designee will take vital signs at screening, prior to the administration of each dose of trial treatment and at treatment discontinuation as specified in the Trial Flow Chart (Section 6.0). Vital signs should include temperature, pulse, respiratory rate, weight and blood pressure. Height will be measured at screening only. BP reading should be obtained 1 week after starting lenvatinib. Patients can either purchase a blood pressure cuff and the study team will train the subject on obtaining a BP at home, or it can be done by community health provider, as long as values are reported) and anti-hypertensives started if the systolic is ≥ 140 or diastolic is ≥ 90 or drug held per Section 5.2.2.6. The treating physician will prescribe anti-hypertensives.

7.1.2.5 Electrocardiograms

Electrocardiograms will be obtained as specified in the Trial Flow Chart (Section 6.0). Complete, standardized, 12-lead ECG recordings that permit all 12 leads to be displayed on a single page with an accompanying lead II rhythm strip below the customary 3×4 lead format are to be used. In addition to a rhythm strip, a minimum of 3 full complexes should be recorded from each lead simultaneously. Participants must be in the recumbent position for a period of 5 minutes prior to the ECG.

7.1.2.7 Urine Dipstick

Urine dipstick testing will be performed locally within 3 days prior to start of treatment. Participants with >1+ proteinuria on urine dipstick during screening will undergo 24-hour urine collection for quantitative assessment of proteinuria. Participants with urine protein ≥ 1 g/24-hour will not be eligible.

Once participants are allocated, urine dipstick testing for participants with proteinuria $\geq 2+$ should be performed on Day 15 (or more frequently as clinically indicated) until the results have been 1+ or negative for 2 consecutive treatment cycles. Urine dipstick testing should be performed at the investigational site. If a new event of proteinuria $\geq 2+$ occurs, the participant must resume the Day 15 urine dipstick testing for evaluation of proteinuria until results are 1+ or negative for 2 consecutive treatment cycles.

For participants with proteinuria $\geq 2+$, see Section 5.2.2.7.

7.1.2.8 Eastern Cooperative Oncology Group (ECOG) Performance Scale

The investigator or qualified designee will assess ECOG status (see Appendix 1) at screening, prior to the administration of each dose of trial treatment and discontinuation of trial treatment as specified in the Trial Flow Chart.

7.1.2.9 Tumor Imaging and Assessment of Disease

Extracranial tumor imaging is strongly preferred to be acquired by CT. For the abdomen and pelvis, contrast-enhanced MRI may be used when CT with iodinated contrast is contraindicated, or when local practice mandates it. Brain imaging is required for all participants. Brain imaging will be done by MRI only. Patients unable to undergo brain MRI are not eligible. The same imaging technique and modality, ideally the same scanner type, and the use of contrast should be used in a participant throughout the study to optimize the reproducibility of the assessment of existing and new tumor burden and improve the accuracy of the assessment of response or progression based on imaging.

Expedited confirmation of measurable disease based on mRECIST 1.1 at screening should be used to determine participant eligibility. Confirmation that the participant's imaging shows at least 1 intracranial, previously untreated lesion that is appropriate for selection as a target lesion per mRECIST 1.1 is required prior to participant allocation.

7.1.2.9.1 Initial Tumor Imaging

Initial tumor imaging at Screening must be performed within 28 days prior to the date of allocation. The site study team must review screening images to confirm the participant has intracranial measurable disease per mRECIST 1.1.

The screening images will be reviewed by local radiology at the trial institution per mRECIST 1.1 for eligibility prior to allocation. Brain imaging should be by MRI. Additional CT screening images must also be submitted for evaluation of extracranial disease and must include at least the chest, abdomen, and pelvis. MRI or PET/CT may be substituted for CT scans of these extracranial areas when appropriate.

7.1.2.9.2 Tumor Imaging During the Study

The first on-study imaging assessment for best BMRR by brain MRI should be performed at 6 weeks (42 days ± 7 days) from the date first study dose. Response assessment will be confirmed at 12 weeks. Subsequent tumor imaging should be performed every 12 weeks (84 days ± 7 days) or more frequently if clinically indicated. Imaging timing should follow calendar days and should not be adjusted for delays in cycle starts. Imaging should continue to be performed until disease progression is identified by the Investigator.

Best overall objective response should be confirmed by repeat imaging assessment. Initial best overall response assessment will be done by CT scans (preferred) performed at 6 weeks (42 days \pm 7 days) from the date first study dose. Response assessment will be confirmed at 12 weeks. Subsequent tumor imaging should be performed every 12 weeks (84 days \pm 7 days) or more frequently if clinically indicated. Imaging timing should follow calendar days and should not be adjusted for delays in cycle starts.

Participants who have disease progression may continue on treatment at the discretion of the Investigator and study PI provided they have met the conditions detailed in Sections 5.5.4.

In participants who discontinue study treatment, tumor imaging should be performed at the time of treatment discontinuation (\pm 4 week window). If previous imaging was obtained within 4 weeks prior to the date of discontinuation, then imaging at treatment discontinuation is not mandatory.

In participants who discontinue study treatment without documented disease progression, every effort should be made to continue monitoring their disease status by tumor imaging using the same imaging schedule used while on treatment (every 12 weeks) to monitor disease status until the start of a new anticancer treatment, disease progression, pregnancy, death, withdrawal of consent, or the end of the study, whichever occurs first.

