6.0 TRIAL FLOW CHART

6.1 Study Flow Chart

Trial Period:		Treatment Cycles ^a								EOT ^b	Post-Treatment			Notes
Treatment Cycle/Title:	Main Study Screening Visit	1	2	3	4	To be repeated beyond 8 cycles				Discon	Safety FU ^{b,c}	FU Visits	Survival Follow-Up	
						5	6	7	8					
Scheduling Window (Days):	-28 to -1		± 3	± 3	± 3	± 3	± 3	± 3	± 3	At time of Discon	30 and 90 days post discon	Every 12 weeks post discon	Every 12 weeks	
Administrative Procedures														
Informed Consent	X													Consent form can be signed at any time prior to any protocol-specific screening procedures being performed. Additional consent is required at initial disease progression per RECIST 1.1.
Inclusion/Exclusion Criteria	X													
Demographics and Medical/Surgical History	X													Significant medical/surgical history will be captured for last 10 years.
Prior and Concomitant Medication Review	X	X	X	X	X	X	X	X	X	X	X	X		Concomitant medications will be recorded for 90d after last dose (or for up to 120d after last dose for SAEs).
Pembrolizumab and Lenvatinib Administration		X	X	X	X	X	X	X	X					Pembrolizumab 200 mg Q3W with lenvatinib 20 mg QD; 21-d cycle
Post-study anticancer therapy status											X	X	X	All anticancer therapy will be recorded until time of death or termination of survival follow-up. If a clinic visit is not feasible, follow up information may be obtained via telephone or email.
Survival Status		X	X	X	X	X	X	X	X	X	X	X	X	
Clinical Procedures/Assessments														

Review Adverse Events		X	X	X	X	X	X	X	X	X	X			AEs: monitored up to 90d after last dose. SAEs and pregnancy: monitored up to 120d after last dose, or 30d after last dose if participant starts a new anticancer therapy, whichever is sooner
Full Physical Examination	X													To be performed within 7d of C1D1.
Directed Physical Examination		X	X	X	X	X	X	X	X	X	X	X	X	
Vital Signs and Weight ^d	X	X	X	X	X	X	X	X	X	X				BP and HR will be measured after the participant has been resting for 5 minutes. See Section 5.2.2.6 for management of hypertension and Section 7.1.2.4 for vital signs. Height is measured at Screening only.
ECOG Performance Status	X	X	X	X	X	X	X	X	X	X				
12-lead ECG	X													Single 12-lead ECG. Participants must be in the recumbent position for a period of 5 minutes prior to the ECG. Additional assessments may be performed if clinically indicated.
Laboratory Procedures/Assessments: analysis performed by LOCAL Lab ^g														

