Pregnancy Test – Urine or Serum β-HCG	X	X	X	X	X	X	X	X	X	X	X			Performed within 10 days of C1D1 and prior to all subsequent scheduled visits. Every effort should be made to collect samples at the same time of day. LDH is only required at screening. Urine protein ≥2 requires 24-hour urine collection and D15 re-evaluation per Section 5.2.2.7. Pregnancy test for WOCP to be done within 72 hours days of C1D1.
PT/INR and aPTT	X													
CBC with Differential	X		X	X	X	X	X	X	X	X	X			
Comprehensive Serum Chemistry Panel	X		X	X	X	X	X	X	X	X	X			
Urinalysis	X		X	X	X	X	X	X	X	X	X			
T3, FT4 and TSH	X		X	X	X	X	X	X	X	X	X			
Efficacy Measurements														
Tumor Imaging (MRI brain ^e and CT Chest, Abdomen, Pelvis)	X		X		X				X	X		X	X	Prior scans performed within the screening period but before signing informed consent may be

														used. All imaging visits have a scheduling window of ± 7 d. Intracranial disease progression will be assessed by mRECIST 1.1. Extracranial disease will be assessed by RECIST 1.1. For participants who DC for reasons other than PD, imaging should be performed Q12W. Imaging at EOT is not required if the previous tumor imaging assessment was within 4 weeks prior to the EOT visit. Imaging of any anatomy that shows disease either at screening or in subsequent evaluations will be required and should be submitted.
Tumor Biopsies/Archival Tissue Collection/Correlative Studies														
Archival or Newly Obtained Tissue Collection	X													New tissue will be collected if the patient has a biopsy or resection for any reason while on study; a new consent will be obtained from the subject for use of part of the collected tissue for research.
Correlative Studies Blood Collection ^f		X	X	X			X			X				

a. Participants who continue treatment with lenvatinib beyond approximately 2 years (only if they experience clinical benefit until unacceptable toxicity or disease progression and upon Sponsor consultation and approval) will follow the same SOA except that thyroid labs beyond approximately 2 years will be performed per SOC or as clinically indicated.

b. If EOT visit occurs ~30 days from last dose of study treatment, a 30-day safety follow-up visit is not required. In this situation, all procedures required at the 30-day Safety Visit and EOT are performed once and entered into the EOT visit only. End of treatment will be defined as the date when the participant discontinues all trial treatments.

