7.1.2.9.4 Modified RECIST 1.1 Assessment of CNS Disease

Modified RECIST 1.1 will be used as the primary measure for assessment of intracranial tumor response, date of intracranial disease progression, and as a basis for all protocol guidelines related

to intracranial disease status (eg, discontinuation of study treatment). Up to 5 intracranial, previously untreated target lesion in the brain will be followed for response and progression. Size is considered the tumor's largest diameter. Measurements from multiple lesions are summed to calculate the sum of the diameters (SD). The SD calculated on a baseline scan performed within 28 days of study drug initiation will be used as a reference to determine the objective response of the clinically evaluable lesions. All responses must be confirmed at 12 weeks with an equivalent or better response. Please refer to the original RECIST criteria if further reference is necessary. Please see section 7.1.2.9 for response assessment in patients requiring local therapy while on study.

Measurable disease

Specification of a minimal lesion diameter for measurable lesions reduces the potential for variation in the measurement of smaller lesions due to slice selection and volume averaging. The minimal lesion diameter should be greater than or equal to 2 times the section thickness and a minimum of 5mm. A previously irradiated lesion will not be measured as a target lesion unless it is documented to have progressed since treatment.

Non-measurable disease

Non-measurable lesions at baseline are important in clinical trials because tumor progression may occur at these sites. Non-measurable lesions include enhancing lesions that are less than the specified smallest measurable diameter (5mm when slice thickness is 2.5mm or twice the slice thickness), hemorrhagic or predominantly cystic or necrotic lesions that are difficult to accurately measure and track, and lesions that are indeterminate for metastatic disease. Intrinsic T1- hyperintensity is noted within hemorrhagic lesions that may be misinterpreted as enhancing tumor, and for this reason, the precontrast T1-weighted image must be examined at baseline to prevent this error. Non-measurable lesions should be briefly described on the imaging case report form for each study {Henson, 2008 #303}.

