7.1.2.9.6 Evaluation of Best Overall Response

The Best Overall Response is the best response recorded from the start of the treatment until disease progression/recurrence (taking as reference for progressive disease the smallest measurements recorded since the treatment started). The patient's best response assignment will depend on the achievement of both measurement and confirmation criteria. The best response will take into consideration both the clinically evaluable brain metastases and systemic metastases, and therefore will include measurements from both mRECIST criteria (in the brain) and RECIST criteria (in the body) as follows:

Complete Response (CR): Disappearance of all target lesions in the brain and systemic disease.

Partial Response (PR): Partial response in both the brain and the systemic disease, or if there is PR at one site and SD at the other, the sum of diameters from the brain and systemic disease will be added and the best overall response will be considered PR if there is at least a 30% decrease, taking as reference the baseline sum diameters.

Progressive Disease (PD): Progressive disease in either the brain or the systemic disease will qualify as PD as the best overall response.

Stable Disease (SD): Stable disease in both the brain and systemic disease, or if the sum of diameters from the brain and systemic disease does not qualify for PR or PD (at least a 20% increase in the sum of diameters of target lesions), taking as reference the smallest sum diameters since the treatment started.

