7.1.5.3.2 Follow-up Visits

Participants who discontinue study treatment for a reason other than disease progression will move into the Follow-Up Phase and should be assessed every 12 weeks (84 ± 7 days) by radiologic imaging to monitor disease status. Every effort should be made to collect information regarding disease status until the start of new anti-cancer therapy, disease progression, death, end of the study or if the participant begins retreatment with pembrolizumab and lenvatinib as detailed in Section 5.2.3. Information regarding post-study anti-cancer treatment will be collected if new treatment is initiated.

Participants who are eligible to receive retreatment with pembrolizumab and lenvatinib according to the criteria in Section 5.2.3 will move from the follow-up phase to the Second Course Phase when they experience disease progression.

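### The protocol gives conflicting dates for imaging after a patient stops all treatment without progression, so an early-stopping week-6 brain responder may have no required week-12 confirmation scan

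*Combined protocol and SAP*

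**What the plan says.** **Confirmation.** The first brain MRI "should be performed at 6 weeks (42 days ± 7 days) from the date first study dose" (Section 7.1.2.9.2). Section 7.1.2.9.4 adds: "All responses must be confirmed at 12 weeks with an equivalent or better response". Section 7.1.2.9.6, on overall response, says: "The patient's best response assignment will depend on the achievement of both measurement and confirmation criteria".

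**Waiver.** Section 7.1.2.9.2: "If previous imaging was obtained within 4 weeks prior to the date of discontinuation, then imaging at treatment discontinuation is not mandatory". The flow chart (Section 6.1) repeats it: "Imaging at EOT is not required if the previous tumor imaging assessment was within 4 weeks prior to the EOT visit".

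**Scan timing after stopping without progression.**
- The flow chart's follow-up visit column, in which imaging is marked, is scheduled "Every 12 weeks post discon".
- Section 7.1.5.3.2 says such patients "will move into the Follow-Up Phase and should be assessed every 12 weeks", with a window of 84 ± 7 days and no anchor date.
- Section 7.1.2.9.2 says every effort should be made to keep to the on-treatment imaging schedule, which it describes in parentheses as every 12 weeks. The same section says "Imaging timing should follow calendar days and should not be adjusted for delays in cycle starts".
- Flow-chart footnote e lists brain MRI at weeks 6 and 12 and every 12 weeks after that, without limiting this to patients on treatment.

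**Scoring.** Section 8.3 makes all analyses intent to treat. Section 2.2, note a, limits unevaluable patients to those who miss the 6-week scan without clear clinical CNS progression. Section 5.7, on its face, replaces any participant who discontinues study intervention.

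**The concern.** The primary endpoint depends on one scan at one time. For a patient still on treatment its date is clear. For a patient with a brain response at week 6 who then stops both drugs, for example for toxicity, the date depends on which part of the protocol the site follows. Section 5.2.2.14 does not allow lenvatinib alone after pembrolizumab is stopped for toxicity, so a full stop of this kind is foreseeable.

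A site that follows the flow-chart column, and uses the waiver, has no instruction to image this patient around week 12. Imaging after discontinuation also ends when a new anticancer treatment starts, so a later confirming scan may never be done. A response could then go unconfirmed because of the schedule and not because of the tumour. The decision rules are 4 of 27 and 7 of 29, where single patients can matter. The trial is multi-site, so different sites may follow different readings.

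**Working it through.** **1. How far the waiver reaches.** The week-6 scan falls on day 42 ± 7, that is day 35 to 49. Adding 28 days, the waiver covers a stop through:
- scan on day 35: day 63 (week 9)
- scan on day 42: day 70 (week 10)
- scan on day 49: day 77 (week 11)

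**2. The next required scan.** The week-12 window is day 84 ± 7, that is day 77 to 91.

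| Stop of both drugs | Counted from discontinuation (stop + 84 ± 7) | Counted from first dose |
|---|---|---|
| Day 42 | Day 119–133 (nominal week 18) | Day 77–91 |
| Day 56 | Day 133–147 (nominal week 20) | Day 77–91 |
| Day 70 | Day 147–161 (nominal week 22) | Day 77–91 |

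Counted from discontinuation, no required scan falls in day 77 to 91, and the next comes 6 to 10 weeks after week 12. Counted from first dose, there is no gap.

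**3. The plan's own power (Section 8.2).** With X1 the stage 1 responses in n1 patients, and success defined as at least r responses in n:

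P(success) = Σ over x1 above the futility bound of P(X1 = x1) × P(Bin(n − n1, p) ≥ r − x1)

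- Melanoma: stop at 0 of 13, succeed at 4 or more of 27. This gives 0.0416 at 5% and 0.801 at 20%.
- RCC: stop at 2 or fewer of 18, succeed at 7 or more of 29. This gives 0.801 at 30%. Section 8.2 does not name the null rate; with the 12% it cites for nivolumab, type I error is 0.0497.

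Both stated figures (80% power, 0.05) are reproduced.

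**4. Effect of lost responses.** The documents give no early discontinuation rate. Section 4.2.2 reports dose reduction (62%) and interruption (47.6%) among 21 melanoma patients, which do not measure permanent stops. Let f be the assumed share of true responders who lose confirmation this way and are scored as non-responders. Power is recomputed at p1 × (1 − f). The chance that at least one response is lost is 1 − (1 − p1 × f)^n.

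| f (assumed) | Melanoma: rate, power | At least one lost | RCC: rate, power | At least one lost |
|---|---|---|---|---|
| 0 | 0.200, 0.801 | 0 | 0.300, 0.801 | 0 |
| 2% | 0.196, 0.787 | 10% | 0.294, 0.782 | 16% |
| 5% | 0.190, 0.765 | 24% | 0.285, 0.750 | 35% |
| 10% | 0.180, 0.724 | 42% | 0.270, 0.691 | 59% |

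At f = 10%, the chance of stopping for futility at stage 1 rises from 0.055 to 0.076 (melanoma) and from 0.060 to 0.099 (RCC).

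**The case against.** The strongest case is that the imaging-specific text already settles the matter. The flow-chart window heads a whole visit column, which also covers medication review, physical examination and therapy status. Section 7.1.2.9.2 deals with imaging directly and carries the on-treatment schedule forward, and footnote e lists week 12 with no treatment condition. Footnote c says the 90-day safety visit may be combined with an imaging visit if the two windows coincide; had imaging restarted at discontinuation, day 84 ± 7 would usually cover day 90 and the condition would do little. This supports counting from first dose, and that reading closes the gap.

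It does not remove the conflict. The calendar rule in Section 7.1.2.9.2 concerns delayed cycle starts, not discontinuation. Its parenthesis omits the step from week 6 to week 12. The chart that sites schedule from says something different.

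Other parts of the objection stand in full:
- The waived scan is optional, not barred. The discontinuation scan has a ± 4-week window, so for a stop on day 49 or later it could reach day 77.
- Sections 7.1.2.9.2 (for overall response) and 7.1.2.9.7 ask for confirmation by imaging in more general terms, so a later confirming scan is excluded only on a strict reading of Section 7.1.2.9.4.
- A patient whose treatment is only withheld, or who stops lenvatinib and continues pembrolizumab, has not discontinued all treatment and stays on the ordinary schedule.
- The loss rate is assumed, and the calculation takes the 20% and 30% targets as containing no such attrition already.

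**Conclusion.** The point holds as an internal contradiction about when the primary-endpoint confirmation scan is due, together with silence on how to score a week-6 response that has no week-12 scan. It should be corrected.

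A reader might infer more: that the scan clock does restart at discontinuation, that these patients have no week-12 scan, and that they count as non-responders. The documents do not support this. The restart is one of two readings, the scan is not required on that reading but may still be done, and non-responder status is only an inference from Section 7.1.2.9.4 read with intent to treat. Section 5.7 could equally lead to replacement, which would remove an observed week-6 responder and sits badly with Section 2.2 and with intent to treat. Any late dating of progression for PFS likewise depends on the flow-chart reading.

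The size is unknown. A loss costs power only if a site follows the flow chart, no optional scan is done and the response is scored as a non-response. Under those conditions, assumed losses of 2% to 10% of responders cost 1.4 to 7.7 percentage points of power in melanoma and 1.9 to 11.0 in RCC, taking rounded power from 0.801. The average effect at the low end is small.

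**What to change.** - In Sections 7.1.2.9.2 and 7.1.5.3.2 and in the flow chart, anchor all imaging after discontinuation without progression to first dose: weeks 6 and 12, then every 12 weeks. Stop counting imaging from discontinuation in the follow-up column.
- State that a patient with an unconfirmed response still has the planned week-12 brain MRI and body scan whether or not on treatment, and that the 4-week waiver does not replace it.
- Reconcile Sections 2.2 (note a), 5.7, 7.1.2.9.4 and 8.3 in one rule on how a week-6 response without a week-12 scan is scored, and whether such a patient can be replaced.

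The cost is an amendment to wording. The week-12 scan is already planned for every patient, so the practical burden is a scan pulled forward in a few patients. No dose or treatment rule changes.
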